This study will be a randomized, controlled superiority trial to evaluate a hospital-wide initiative to improve counseling for postpartum women who experienced HDP during their pregnancy or in the immediate postpartum period. Hypotheses: 1. We hypothesize that the prompt will increase the proportion of women counseled on transitioning care to a primary care provider or cardiologist after pregnancy (primary outcome). 2. We hypothesize that the provider nudge will increase the proportion of women attending a preventative care visit within 6 months of delivery as assessed by chart review and patient surveys. The HSM daily log generated through the Way to Health platform will be used to generate lists of patients who eligible for the study. For each eligible woman, the date of and obstetric care provider for her postpartum visit will be recorded within 3 weeks of delivery. Patients will then be randomly assigned to a control group with no intervention (usual care through HSM) or the intervention group (physician nudge) using simple 1:1 randomization through the Way to Health Platform. If a woman is randomized to the intervention arm, her obstetric care provider for her postpartum visit will receive a staff message in Epic (Penn Chart) that his/her patient has an upcoming postpartum visit. The message will be sent 1 week before the scheduled visit. The message will have patient-specific information including hypertensive diagnosis, blood pressure medication(s), gestational diabetes diagnosis, and primary care provider as listed in the Epic banner. The message will also have dot phrases for recommended counseling and contact information for UPHS primary care and cardiology providers. There will be a dot phrase recommending follow-up with primary care or cardiology; counseling on risk of future CVD; and recommending aspirin in a future pregnancy. A web-based survey will be distributed to all women in the study 6 months after delivery through the Way to Health platform. The survey will assess attendance at a preventative care visit, social determinants of health, health status, and insurance status after delivery. Demographic characteristics, medical and obstetric history, hypertensive disorder, laboratory test results (platelet count, creatinine, liver function tests, urine protein, total cholesterol, triglycerides, LDL-C, HDL-C, glucose, hemoglobin A1c), blood pressure measurements, height, weight, and office visits within 6 months of delivery will be abstracted from the EMR. We will perform detailed abstraction of counseling at the postpartum visit and additional office visits within 6 months of delivery focusing on 1) health maintenance 2) hypertension, or 3) cardiovascular risk reduction. Two reviewers will assess counseling at each visit. We will obtain data on obstetric care providers including level (resident physician, attending physician, nurse practitioner, physician assistant, or certified nurse midwife), gender, and years in practice from publicly available databases or websites online.

Study duration

Estimated length of time is 12 months. We believe it will take no more than 4 months to enroll all patients with follow-up survey at 6 months, and allow two months for data analysis. This is based on number of women clinically enrolled over the 1st year of Heart Safe Motherhood at Pennsylvania Hospital. We hope to initiate the proposed study on November 1, 2020.

Resources necessary for human research protection

Describe research staff and justify that the staff are adequate in number and qualifications to conduct the research. Describe how you will ensure that all staff assisting with the research are adequately informed about the protocol and their research related duties. Please allow adequate time for the researchers to conduct and complete the research. Please confirm that there are adequate facilities for the research.

The research staff will include Maternal Fetal Medicine attendings, residents in obstetrics & gynecology, and the Maternal and Child Health Research (MCHRC) clinical research team. The MCHRC provides an established infrastructure for clinical and translational research. The Way To Health platform has multiple features to implement this trial and capture data including two-way texting, integrated survey options, integration with the EMR, and automated schedules for patient messages. Patients will be clinically

enrolled into the WaytoHealth Texting Platform per usual clinical care. Data collection will be performed by Drs. [name] and [name], and by a study coordinator through the MCHRC. Patient logs for Heart Safe Motherhood (Way to Health) will be reviewed daily. Randomization will take place through Way to Health after ensuring all eligibility criteria is met. Electronic prompts will be sent to obstetric care providers by [name] or the study coordinator. Survey invitations will be sent through the Heart Safe Moterhood interface in Way to Health. All research staff will receive education regarding the protocol and their duties prior to the start of the study.

Characteristics of the Study Population

Target population

Postpartum women followed by obstetric care providers at the University of Pennsylvania Health System (UPHS) who are diagnosed with HDP and are clinically enrolled in Heart Safe Motherhood (HSM) are eligible.

Subjects enrolled by Penn Researchers 222

Subjects enrolled by Collaborating Researchers

0

Accrual

Sample size calculations were based on the assumption that 21% of patients in usual care and 40% of patients receiving a provider nudge would have documentation about transitioning care. A sample size of 222 patients (randomized 1:1) would provide 80% power to detect this difference assuming 20% of patients will not attend their postpartum visit. Approximately 100 women are enrolled in HSM each month at Pennsylvania Hospital. We anticipate that over 90% of those women receive prenatal care at a UPHS practice (n=90 per month), and at least 80% will attend a postpartum visit (n=72). We thus anticipate that 222 women could be enrolled in 3-4 months, allowing for 6-month follow-up during the grant period.

Key inclusion criteria

1. At least 18 years old. 2. Have a diagnosis of HDP during delivery admission or have a diagnosis made at time of evaluation in the Perinatal Evaluation and Treatment Unit after discharge from the delivery admission. HDP diagnoses are based on criteria from the American College of Obstetricians and Gynecologists (ACOG). 3. Enrolled in HSM at Pennsylvania Hospital. 4. Have a postpartum visit with a UPHS provider scheduled 4-12 weeks after delivery.

Key exclusion criteria

1. Women diagnosed with chronic hypertension (CHTN) without superimposed pre-eclampsia (PEC).

Vulnerable Populations

Children Form

Pregnant women (if the study procedures may affect the condition of the pregnant woman or fetus) Form

Fetuses and/or Neonates Form

Prisoners Form

Other x None of the above populations are included in the research study

The following documents are currently attached to this item:

There are no documents attached for this item.

Populations vulnerable to undue influence or coercion

This is a hospital-wide initiative which will equally include all postpartum women in HSM who do not meet exclusion criteria.

Subject recruitment

The HSM daily log generated through the Way to Health platform will be used to generate lists of patients who eligible for the study. For each eligible woman, the date of and obstetric care provider for her postpartum visit will be recorded within 3 weeks of delivery.

Will the recruitment plan propose to use any Penn media services (communications, marketing, etc.) for outreach via social media avenues (examples include: Facebook, Twitter, blogging, texting, etc.) or does the study team plan to directly use social media to recruit for the research?

No

The following documents are currently attached to this item:

There are no documents attached for this item.

Subject compensation*

Will subjects be financially compensated for their participation?

Yes

The following documents are currently attached to this item:

There are no documents attached for this item.

If there is subject compensation, provide the schedule for compensation per study visit or session and total amount for entire participation, either as text or separate document

Subjects who complete a web-based survey 6 months postpartum will be compensated with a \$5 giftcard.

Study Procedures

Suicidal Ideation and Behavior

Does this research qualify as a clinical investigation that will utilize a test article (ie- drug or biological) which may carry a potential for central nervous system (CNS) effect(s)?

No

Procedures

A flowsheet of patient participation is attached. Subjects will be identified through the HSM daily log. A waiver of informed consent is requested for the intervention portion of this study. At 30 days after discharge, all participants, regardless of study arm will receive the following message "Hello from Heart Safe Motherhood! We hope you are doing well. Dont forget to follow-up with your primary or heart doctor in the next 2-4 weeks. If you were given an appointment, make sure to keep it. If you want to make an appointment with a heart doctor focused on women's health, call [contact]. Have a great day!" At 6 months postpartum, women will receive a secure text message through the Way To Health platform. "We are trying to understand how women with high blood pressure or preeclampsia stay healthy after delivery. Respond yes if you are willing to complete a survey. You will receive \$5 for participating." If she responds yes, she will receive a survey link integrated with Way To Health. Patient information will be obtained from the electronic medical record including demographic characteristics, medical and obstetric history, hypertensive disorder, laboratory test results (platelet count, creatinine, liver function tests, urine protein, total cholesterol, triglycerides, LDL-C, HDL-C, glucose, hemoglobin A1c), blood pressure measurements, height, weight, and office visits within 6 months of delivery. We will perform detailed abstraction of counseling at the postpartum visit and additional office visits within 6 months of delivery focusing on 1) health maintenance 2) hypertension, or 3) cardiovascular risk reduction. Two reviewers will assess counseling at each visit (from the discharge summary and after visit summary). We will obtain data on obstetric care providers including level (resident physician, attending physician, nurse practitioner, physician assistant, or certified nurse midwife), gender, and years in practice from publicly available databases or websites online.

The following documents are currently attached to this item:

There are no documents attached for this item.

Deception

Does your project use deception?

No

International Research

Are you conducting research outside of the United States?

No

Analysis Plan

We hypothesize that a provider nudge will increase the proportion of women who are counseled about 1) transitioning care and 2) CVD risk after pregnancy complicated by HDP. This is designed as a superiority trial. We hypothesize that the provider nudge will lead to improved follow-up with continuity care providers. Primary efficacy endpoint: 1. Documentation of counseling about transitioning care to a continuity care provider (primary care or cardiology) at the postpartum visit. Secondary efficacy endpoints: 1. Documentation of CVD risk at the postpartum visit. 2. Attendance at a primary care or cardiology visit for preventative care within 6 months of delivery. Chi square or Fishers exact test will be used to compare categorical data. T-test will be used to compare parametric data. Mann-Whitney U test will be used to compare non-parametric data. Univariate comparisons will be made between exposure (intervention) and outcome. Proportion and relative risk (95% CI) will be presented for primary and secondary outcomes. Multivariable logistic regression models will be created to control for potential confounders. Outcomes will be analyzed by the intention to treat principle. Our threshold for statistical significance will be two-side with alpha 0.05. Exploratory analyses: Primary and secondary outcomes will be analyzed by race (Black vs. Non-Black) based on data that HSM reduced racial disparities in blood pressure ascertainment outcomes. We will explore whether there is an interaction of race with regards to counseling and follow-up. We will also assess time trends in counseling over the study period.

The following documents are currently attached to this item:

There are no documents attached for this item.

Data confidentiality

- Paper-based records will be kept in a secure location and only be accessible to personnel involved in the study.**
- Computer-based files will only be made available to personnel involved in the study through the use of access privileges and passwords.**
- Prior to access to any study-related information, personnel will be required to sign statements agreeing to protect the security and confidentiality of identifiable information.**
- Wherever feasible, identifiers will be removed from study-related information.**
- A Certificate of Confidentiality will be obtained, because the research could place the subject at risk of criminal or civil liability or cause damage to the subject's financial standing, employability, or liability.**
- A waiver of documentation of consent is being requested, because the only link between the subject and the study would be the consent document and the primary risk is a breach of confidentiality. (This is not an option for FDA-regulated research.)**
- Precautions are in place to ensure the data is secure by using passwords and encryption, because the research involves web-based surveys.**
- Audio and/or video recordings will be transcribed and then destroyed to eliminate audible identification of subjects.**

Subject Confidentiality

Computer-based files will only be made available to personnel involved in the study through the use of access privileges and passwords. Wherever feasible, identifiers will be removed from study-related

information. Precautions are already in place to ensure the data are secure by using passwords and HIPAA-compliant encryption. Data on patients will be obtained from Epic and patient-completed surveys. Any information that is obtained will be used for research purposes only. Information on patients will only be disclosed within the study team and to the patients obstetric care provider. All study staff will be reminded of the confidential nature of the data collected and contained in these databases. All members that access data must complete HIPAA training including secure data transfer, passwords, computer security habits and knowledge of what constitutes misuse or inappropriate use of the server. Only trained study staff will have access to the code that links the unique identifier to the subjects identity. Electronic data will be stored on secure, password-protected firewalled servers at the University of Pennsylvania. Data collected for this study will be stored in REDCap and the WayToHealth platform. Linkage to PHI will be stored until study analysis and publication completion, and then will be destroyed.

Sensitive Research Information*

Does this research involve collection of sensitive information about the subjects that should be excluded from the electronic medical record?

No

Subject Privacy

Privacy refers to the person's desire to control access of others to themselves. Privacy concerns people, whereas confidentiality concerns data. Describe the strategies to protect privacy giving consideration to the following: The degree to which privacy can be expected in the proposed research and the safeguards that will be put into place to respect those boundaries. The methods used to identify and contact potential participants. The settings in which an individual will be interacting with an investigator. The privacy guidelines developed by relevant professions, professional associations and scholarly disciplines (e.g., psychiatry, genetic counseling, oral history, anthropology, psychology).

All efforts will be made by study staff to ensure subject privacy. Data will be evaluated in a deidentified manner whenever possible.

Data Disclosure

Will the data be disclosed to anyone who is not listed under Personnel?

No

Data Protection*

- Name**
- Street address, city, county, precinct, zip code, and equivalent geocodes**
- All elements of dates (except year) for dates directly related to an individual and all ages over 89**
- Telephone and fax number** **Electronic mail addresses**
- Social security numbers**
- Medical record numbers**
- Health plan ID numbers**
- Account numbers**
- Certificate/license numbers**
- Vehicle identifiers and serial numbers, including license plate numbers**
- Device identifiers/serial numbers**
- Web addresses (URLs)**
- Internet IP addresses**
- Biometric identifiers, incl. finger and voice prints**
- Full face photographic images and any comparable images**
- Any other unique identifying number, characteristic, or code**
- None**

Does your research request both a waiver of HIPAA authorization for collection of patient information and involve providing Protected Health Information ("PHI") that is classified as a "limited data set" (city/town/state/zip code, dates except year, ages less than 90 or aggregate report for over 90) to a recipient outside of the University of Pennsylvania covered entity?

No

Tissue Specimens Obtained as Part of Research* Are

Tissue Specimens being obtained for research?

No

Tissue Specimens - Collected during regular care*

Will tissue specimens be collected during regular clinical care (for treatment or diagnosis)?

No

Tissue Specimens - otherwise discarded* Would

specimens otherwise be discarded?

No

Tissue Specimens - publicly available* Will

tissue specimens be publicly available?

No

Tissue Specimens - Collected as part of research protocol* Will

tissue specimens be collected as part of the research protocol?

No

Tissue Specimens - Banking of blood, tissue etc. for future use* Does

research involve banking of blood, tissue, etc. for future use?

No

Genetic testing

If genetic testing is involved, describe the nature of the tests, including if the testing is predictive or exploratory in nature. If predictive, please describe plan for disclosing results to subjects and provision of genetic counseling. Describe how subject confidentiality will be protected Note: If no genetic testing is to be obtained, write: "Not applicable." Not applicable.

Consent

1. Consent Process

Overview

A waiver of informed consent is requested for the intervention portion of this study. This is a hospitalwide initiative that will be implemented. The study is to evaluate that initiative. Therefore, physicians and their patients will not be consented as this will be the standard practice for women in Heart Safe Motherhood at Pennsylvania Hospital. Without a waiver of the consent, the initiative would still be implemented at Pennsylvania Hospital, but the study would be infeasible. There are several additional reasons why we feel a waiver of consent should be granted. First, it is not feasible to consent every patient and physician. Second, if members of the control group were consented, they would know they were being studied and this could change their behavior. This could potentially disrupt the design of the study and making interpretation of the findings challenging. Third, physicians are not being forced to use the information from the prompt or suggested counseling with their patients. Instead, they are being reminded of evidence-based practice and offered an opportunity to review pertinent information prior to the postpartum visit. This is no different than standard of care in which a physician would review the same information and decide on postpartum counseling. The initiative is simply a reminder for the physician and makes their standard of care process easier to conduct.

Children and Adolescents

Children and adolescents will not be enrolled.

Adult Subjects Not Competent to Give Consent

All adult subjects will be competent to give informed consent.

2. Waiver of Consent

Waiver or Alteration of Informed Consent*

Waiver of written documentation of informed consent: the research presents no more than minimal risk of harm to subjects and involves no procedures for which written consent is normally required outside of the research context

Minimal Risk*

Impact on Subject Rights and Welfare*

Waiver Essential to Research*

Additional Information to Subjects

Written Statement of Research*

Yes

If no written statement will be provided, please provide justification

The subjects will receive a written statement of research for the web-based survey, but will not receive a statement on research for the intervention as knowledge of the intervention may change behavior and make interpretation of the study difficult.

The following documents are currently attached to this item:

There are no documents attached for this item.

Risk / Benefit

Potential Study Risks

The potential risks associated with this study are minimal. Breach of data is a potential risk that will be mitigated by using HIPAA compliant and secure data platforms for patient identification, randomization, and web-based surveys (Way to Health) and data storage (REDCap).

Potential Study Benefits

An intervention that prompts obstetric care providers to actively think about postpartum care guidelines could contribute positively to patient care and outcomes. However, it is possible that patients will receive no benefit from this study.

Alternatives to Participation (optional)

Women will receive postpartum counseling per the usual practice of their obstetric care provider.

Data and Safety Monitoring

Principal investigator.

The following documents are currently attached to this item:

There are no documents attached for this item.

Risk / Benefit Assessment

There is minimal risk to participation in this study with potential for improved counseling and transitions of care.

General Attachments

The following documents are currently attached to this item:

[Additional forms \(citi-[name].pdf\)](#) [Additional forms \(citi2-[name].pdf\)](#) [Additional forms \(citi3-[name].pdf\)](#)

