HDP. A significant proportion of women with HDP do not see a preventative care provider (primary care, cardiology) in the months after delivery.¹⁰⁻¹² Black women are particularly vulnerable to being lost to follow-up after complicated pregnancy.^{10,11} The HSM program is an innovative, patient-centered program that monitors postpartum blood pressure remotely using a text-based interface. It is supported by the Way to Health platform. HSM improves blood pressure management in the two weeks after delivery and eliminates racial disparities in blood pressure ascertainment during that time.^{13,14} However, enrollment in HSM did not improve follow-up in the year after delivery, with less than 1/3 of women having a preventative care visit.¹⁵ Poor follow-up is likely multifactorial, but may be driven by inadequate patient counseling in the postpartum period. Among women enrolled in HSM, only 21% of women were counseled on follow-up with primary care and only 4% were counseled on CVD risk at their postpartum visits based on chart review.¹⁶ Nudges are effective for changing medical decision-making and improving clinical outcomes. Nudges utilize concepts from behavioral economics to subtly change the decision-making environment to facilitate evidence-based care and can be delivered to patients, providers, or both.¹⁷ Examples of nudges include electronic prompts to order cancer screening and electronic defaults that guide ordering practices.¹⁸ Nudges are low cost, scalable using Electronic Medical Record (EMR) systems, and improve rates of preventative services including influenza vaccination, referral to mammography, and statin prescription for CVD prevention.¹⁹⁻²²

References:

1. American College of Obstetricians and Gynecologists; Task Force on Hypertension in Pregnancy. Executive summary: hypertension in pregnancy. *Obstet Gynecol* 2013;122:1122-31.

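### Does the 6-month attendance endpoint need a written rule for combining chart review with the opt-in survey?

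*Combined protocol and SAP*

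**What the plan says.** The Design section states the second hypothesis as an effect on attendance: the nudge will "increase the proportion of women attending a preventative care visit within 6 months of delivery as assessed by chart review and patient surveys". It provides for abstraction of office visits within 6 months from the medical record, with no opt-in. It also sends a web survey to all women in both arms at 6 months: "The survey will assess attendance at a preventative care visit, social determinants of health, health status, and insurance status after delivery".

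Under Procedures, the survey invitation is a text message, "Respond yes if you are willing to complete a survey", and the link follows only after a yes.

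The secondary outcomes and the Analysis Plan both list the endpoint as "Attendance at a primary care or cardiology visit for preventative care within 6 months of delivery", without naming a source. The Analysis Plan compares proportions by chi-square or Fisher's exact test, reports relative risks with 95% confidence intervals, and adds: "Outcomes will be analyzed by the intention to treat principle".

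No section says whether one positive source is enough, which source prevails on disagreement, or how a woman with no charted visit and no survey is classed. The two-reviewer step concerns counseling and does not settle this.

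**The concern.** One yes/no endpoint has two measurements, and one of them will be partial unless every woman opts in. At least four rules can be imagined:

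- **A:** chart only.
- **B:** a visit in either source counts; otherwise not attended.
- **C:** survey responders only.
- **D:** either source, with women who have no charted visit and no survey treated as missing.

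On the same data these give different attendance levels and can fall on different sides of 0.05. If the rule were picked after the results were known, the error rate for this endpoint would exceed its nominal 5%. Attendance is also one of only two numbered hypotheses in the Design section, and it is the patient-level result that the nudge is meant to produce.

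**Working it through.** **The plan's own figure.** The plan gives no number for attendance. Its 222 belongs to the primary outcome and can be reproduced with unpooled variance: (1.960 + 0.842)² × (0.21×0.79 + 0.40×0.60) / 0.19² = 88.25, so 89 per arm; 178 / 0.8 = 222.5. It does not bear on the present question.

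**Which rules fit the text.** The hypothesis names both sources and concerns a proportion of women. Intention to treat favours keeping everyone randomised.

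- C discards the chart and every survey non-responder.
- D removes randomised women because they have no charted visit and did not reply.
- A keeps all women but ignores the survey that the Design section names.
- B uses both sources and keeps all 222 women.

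B is the natural reading, and A is the only close competitor.

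**Inputs.** n = 111 per arm (222 randomised 1:1) and two-sided 0.05 come from the plan. The rest are assumptions:

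- True attendance p = 0.33. The Background reports that "enrollment in HSM did not improve follow-up in the year after delivery, with less than 1/3 of women having a preventative care visit", but that covers a year rather than 6 months.
- Chart capture of true visits c = 0.8 (range 0.6 to 1).
- Survey response r = 0.5 (range 0.3 to 0.7), unrelated to attendance.
- Self-report accurate.

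**Expected level.**

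- A = p·c = 0.33 × 0.8 = 26.4%.
- B = p·[c + (1−c)·r] = 0.33 × (0.8 + 0.2×0.5) = 29.7%.

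**Women with no charted visit and no survey.** (1−r)·[(1−p) + p·(1−c)] = 0.5 × (0.67 + 0.066) = 0.368, or about 82 of 222 (45 to 125 over the ranges). They split as follows:

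- True non-attenders: 0.5 × 0.67 = 0.335, about 74 women, whom B classes correctly.
- Attenders missed by both sources: 0.5 × 0.066 = 0.033, about 7 women. The range runs from 0 (c = 1) to 0.7 × 0.33 × 0.4 × 222, about 21 (c = 0.6, r = 0.3).

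So the 82 do not lack data: each has a reviewed chart.

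**Error rate, no true effect.** Simulated chi-square tests, 400,000 trials:

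| c, r | A alone | B alone | A or B, whichever is significant |
|---|---|---|---|
| 0.8, 0.5 | 4.9% | 4.9% | 6.7% |
| 1.0, 0.5 | 5.0% | 5.0% | 5.0% |
| 0.6, 0.7 | 4.9% | 5.0% | 7.9% |

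(At c = 1 the two rules coincide.)

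**Unequal response, no true effect.** With 50% v 60% response and c = 0.8, B gives 29.7% v 0.33 × (0.8 + 0.2×0.6) = 30.4%, and rejects in 5.1% of trials.

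**With a true effect.** For an assumed 33% v 50%, power is 58% for A and 65% for B, and they disagree on significance in 14% of trials. For 33% v 40% they disagree in 8%.

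**Limit of rule B.** Its relative risk is preserved only if capture and response are equal by arm and self-report has no false positives. With self-report sensitivity and specificity of 0.9, B = p·[c + (1−c)·r·0.9] + (1−p)·r·0.1:

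- p = 0.33: 0.2937 + 0.0335 = 32.7%.
- p = 0.50: 0.445 + 0.025 = 47.0%.

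The ratio is 1.44 against a true 0.50/0.33 = 1.52. Over-reporting pulls the estimate toward 1. It can also lift the level above the truth: at r = 0.7 and p = 0.33, B is 35.2%.

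**The case for a change.** The strongest case for a change is that the rule is not written and would cost two or three sentences. Intention to treat governs analysis by assigned arm and does not itself say whether an unobserved visit is a no or a missing value. If all four rules are treated as open, reporting whichever is significant takes the error from 5% to 11.1% at the base case (8.5% to 12.5% over the ranges). Under 33% v 50%, rules A to C disagree on significance in 38% of trials. Rule D is also fragile: with 50% v 60% response and no effect it rejects in 7.8% of trials.

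The omission stands, and so does the arithmetic. The reach of the larger figures does not. They need C or D, which fit the stated sources and the intention-to-treat sentence poorly, and they assume deliberate selection after the results are known. Disagreement between two valid rules under a true effect reflects their different power; it is not an error in either.

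Nor does the wording "additional office visits within 6 months of delivery focusing on 1) health maintenance 2) hypertension, or 3) cardiovascular risk reduction" narrow the attendance source. It belongs to the sentence on abstracting counseling; the sentence on abstracting office visits carries no such focus.

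**Conclusion.** No change follows. This is missing detail that an analyst would fill sensibly: a visit in either source counts as attended, anything else as not attended, with all randomised women in the denominator. The realistic ambiguity is between that rule and chart only. Under the assumed 33% attendance, 80% capture, 50% response unrelated to attendance and accurate self-report, it is worth at most 1.7 points of false-positive risk (6.7% against 5%), none if the chart is complete, and 2.9 points at the least favourable inputs tried. Those are upper bounds that require choosing the rule after seeing the results.

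Capture and response rates are not in the documents, so the sizes are illustrative. The result should be read as recorded or self-reported attendance, and over-reporting would bias the ratio toward 1. The primary outcome and the sample size are unaffected.
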